4.3 JUSTIFICATION FOR INTERVENTION

From a patient-centered perspective, reducing the burden of disease (e.g., medication dosage, diabetes self-monitoring, and diabetes distress) has a direct impact on the individual. From a health system perspective, if those with T2DM cost approximately \$7,700 more annually to care for than those without T2DM⁷, inducing remission saves \$23,100 over 3 years. Based on data from the DiRECT trial, the absolute risk reduction (ARR) at 2 years is 33%; therefore, the number needed to treat (NNT) to achieve one remission is 3 ($1 \div \text{ARR}$). Comparatively, the well-accepted Diabetes Prevention Program had an overall absolute risk reduction of 14.3% compared to placebo, with a NNT of 7.¹⁹ Even if the ARR is adjusted based on modifying the population of patients included in such an intervention (e.g., including people on insulin), an ARR of 20% is still superior to the Diabetes Prevention Program.

To make this type of intervention accessible, we need to demonstrate a model of delivery that is scalable and sustainable. Our application addresses this specific challenge. The Wake Forest Baptist Health Weight Management Center (WMC) has the expertise and infrastructure to deliver total meal replacement diets designed to achieve higher percentages of weight loss. We have demonstrated previously that our mean weight loss achieved in all-comers is higher than that reported in the DiRECT trial. We have also reported improvements in glycemic control and diabetes remission rates. Our intent with this proposal is to pair our proven treatment programs with a digital platform designed to provide a tailored treatment experience that is scalable and sustainable.

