6.3 MEASURES TO MINIMIZE BIAS: RANDOMIZATION AND BLINDING

Participants will be randomized using a web-based protocol for treatment assignment. Once participants are screened as eligible to participate, the study coordinator will submit the participant's study number for treatment assignment via the study web portal. Randomization will be done in blocks of 10, stratified by sex.

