Demographics: Demographic information including sex, race/ethnicity, and date of birth (age) will be captured at the first screening visit during verification of eligibility. Medical history including date of

diabetes diagnosis (duration of diabetes) and co-morbid conditions will be captured by interview and verification from the medical record when available.

Dietary intake: To assess **dietary intake**, we will use NCI's automated, self-administered 24-hour dietary recall, the Automated Self-Administered 24-hour (**ASA24**®) dietary assessment tool (version: ASA24-2018). The ASA24-2018 will be completed on three, non-consecutive days (including one weekend day) at baseline (pre-randomization), and again at months 3, 6, and 12. The ASA24-2018 is available for use on computers and mobile devices. At the baseline visit, participants will complete one ASA24 assisted by a research staff member. They will then be asked to complete a second and third ASA24 during run-in, on their own, as a part of the baseline assessment. During office visits at each relevant follow-up time point (3, 6 and 12 months), participants will again complete the ASA24. Following each of these visits, a staff member will contact participants within six days (on a randomly selected day) to inform them to complete 2 additional dietary recalls and will offer to conduct the recall over the phone if needed (the ASA24 performs equally well as a self- or interviewer- administered questionnaire).^{23,24} Follow-up reminder calls will be made to encourage completion of the recalls if not completed within 24-hours following a contact. Using the ASA24 data from each time point (baseline, 3, 6, and 12 months), specific outcomes of interest will include: **total daily energy intake** (kcal; averaged across 3 days), **macronutrient composition** of diet (%Carbohydrate/Fat/Protein; averaged across 3 days), **number of eating episodes** per day, and **Healthy Eating Index (HEI)-2015** score (a validated summary measure of dietary quality, rated on a 100-point scale,^{25,26} which is sensitive to change with dietary intervention^{26,27}, and can be calculated using publicly-available SAS code from the ASA24 website).

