Physical activity: We will use pedometers to assess objective physical activity (PA) – operationalized as **daily step counts** – at baseline, 3, 6, and 12 months. Although accelerometry is the gold standard for objective PA measurement,²⁸ pedometers have 99.8% step count accuracy, particularly when worn at the hip.^{29,30} For our study, participants will be fitted with a pedometer and asked to wear it for all waking hours (except while bathing or water activities) over their right hip for 7 consecutive days at each relevant time point in follow-up. At the end of the 7th day, participants will open the unit, record the final step count, and return the pedometer to WFSOM via a pre-stamped mail envelope. **Self-report:** In order to compare our results with the extant literature that has used self-reported PA outcomes, we will also include the short form of the IPAC, a self-report instrument with good reliability (Spearman's rho=0.8) and criterion validity comparable to other self-report instruments.³¹

Diabetes medication class/dose: All medications will be assessed quarterly as previously described. Variables of interest include medication name, total dose, and class of medication at baseline and longitudinal changes during the trial follow up.

Healthcare utilization and quality of life: To capture differences in quality of life associated with the intervention arm, we will use EuroQol's EQ-5D-5L instrument as the quality measure³². This instrument takes responses to five questions on mobility, self-care, ability to perform usual activities, pain, and anxiety/depression to produce a validated quality score (0 to 1). This instrument will be administered at baseline and at the end of the study (12 months). We anticipate no patient deaths during the study period; as such, we will treat the difference in the quality score at the end of the study period and at baseline as the change in the quality of life year (QALY). For instance, if the quality score is 0.4 at baseline and 0.6 at the study-end, the change in the quality of life will be 0.2 QALYs.

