9.4 STATISTICAL ANALYSES

9.4.1 GENERAL APPROACH

Analyses: In general, two types of analyses will be performed: 1) those aimed at estimation of the difference between intervention groups for outcomes like percent change in body weight and HbA1c, and 2) those aimed at estimating differences in the proportion of participants achieving remission by treatment arm. We will analyze the data based on intention to treat principles. Analysis of covariance will be used to estimate the effect of the intervention on 12-month continuous measures including body weight percent change and HbA1c. The model to be used will include the following covariates: the baseline value of the outcome, gender, and age (to control for possible imbalance due to the small number of participants randomized). 95% confidence intervals will be generated for the intervention effect on these and other outcomes. The proportion of remission between two groups will be compared using a two-sided chi-square test and summarized using an odds ratio (OR) and confidence intervals (CI). The primary outcome will be percent change in initial body weight. Secondary outcomes include change in HbA1c and diabetes status (remission will be indicated by a dichotomous yes or no).

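### The 12-month HbA1c ANCOVA leaves out baseline insulin use, which is already recorded; adding it is a cheap gain in precision and does not repair an invalid analysis

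*Combined protocol and SAP*

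**What the plan says.** Section 9.4.1 applies ANCOVA to "12-month continuous measures including body weight percent change and HbA1c". It lists the covariates: "The model to be used will include the following covariates: the baseline value of the outcome, gender, and age (to control for possible imbalance". The reason given is "to control for possible imbalance due to the small number of participants randomized". Remission is handled separately in the same section, by an unadjusted two-sided chi-square test with an odds ratio.

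On balance by design, Section 6.3 says: "Randomization will be done in blocks of 10, stratified by sex".

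On insulin users, neither Section 5.1 nor Section 5.2 excludes them. Section 6.1.1 names insulin use among the features of a participant's regimen that shape follow-up in the active arms, and lets platform content differ between people on insulin and people on metformin alone. Section 6.5.1 contains a rule for participants who are on insulin.

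On data, Section 8.1 already collects what is needed: "Variables of interest include medication name, total dose, and class of medication at baseline".

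**The concern.** The covariate list has a declared job, which is to protect a 90-person trial against chance imbalance. Measured against that job it has a visible gap. Insulin use is a baseline characteristic that the protocol itself uses to steer care, and neither stratification nor the model deals with it.

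Baseline HbA1c may not stand in for it. HbA1c is measured on treatment, so two people with the same baseline value, one on insulin and one on metformin alone, may have different expected values at 12 months once weight loss and medication changes begin. If so, a chance difference between arms in the share of insulin users moves the HbA1c estimate in that particular trial, and the variation it causes stays in the residual and widens the interval. The hypothesis exposed is H2a in Section 9.1, that HIWL with or without CGM lowers HbA1c more than DSME.

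**Working it through.** **1. The plan's own figure, and whether the primary outcome is touched.** Section 9.2 gives 15% against 3% weight loss (difference 12 points), SD 6.8, 30 per arm, loss up to 20%, and power above 95%. With 24 analysed per arm and two-sided alpha 0.05 (assumed; Section 9.2 does not state it), the noncentral t gives power 0.99997, so the stated figure is reproduced. Now add insulin use, with an assumed effect g of 1–5 points of weight loss and a share p of 10–30%:
- R² = g²·p(1−p)/6.8², from 1 × 0.09/46.24 = 0.002 to 25 × 0.21/46.24 = 0.11
- adjusted SD = 6.8·√(1−R²), from 6.79 down to 6.40
- power stays above 0.9999 throughout

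The primary weight result does not depend on this choice.

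**2. Inputs for HbA1c.** Arm sizes come from Section 4.1 and the synopsis: 90 participants, 30 per arm. H2a is read as both HIWL arms (60) against DSME (30). The rest is assumed, because the documents give none of it: insulin users p = 10–40%; effect g = 0.3, 0.5 or 1.0 HbA1c points at equal baseline HbA1c; residual SD of the planned model = 1.0. Insulin use is taken as unrelated to baseline HbA1c, gender and age. If it is related, those terms already absorb part of it and the gains below are smaller.

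**3. How large is chance imbalance?** Spread 90p users at random over 60 and 30 places (hypergeometric) and take the absolute difference in share:

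| Users | Mean difference | Difference of 15 points or more |
|---|---|---|
| 10% | 5.2 points | 6% of trials |
| 20% | 7.0 points | 16% |
| 30% | 8.1 points | 22% |
| 40% | 8.7 points | 25% |

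**4. Shift in the HbA1c estimate.** Shift = imbalance × g.
- Average imbalance: 0.05 × 0.5 = 0.025, up to 0.09 × 1.0 = 0.09, so about 0.03–0.09 points
- 15-point imbalance: 0.15 × 0.5 = 0.075, up to 0.15 × 1.0 = 0.15 points
- Standard error: 1.0 × √(1/60 + 1/30) = 0.22; after 20% loss (48 against 24), 0.25

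The average shift is about 0.1–0.4 of a standard error (0.025/0.22 to 0.09/0.22). The 15-point case is about 0.3–0.7.

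**5. Precision gained by adjusting.** Share of residual variance removed: v = p(1−p)g²/1.0². Equivalent gain in sample size: 1/(1−v) − 1.

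| p | g | v | Gain |
|---|---|---|---|
| 0.2 | 0.5 | 0.04 | 4% |
| 0.3 | 0.5 | 0.05 | 6% |
| 0.2 | 1.0 | 0.16 | 19% |
| 0.3 | 1.0 | 0.21 | 27% |
| 0.2 | 0.3 | 0.014 | 1.5% |
| 0.3 | 0.3 | 0.019 | 1.9% |

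The top of the range needs both 30% users and a full 1.0-point effect.

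**The case against.** The strongest reply is that nothing here is an error. A randomized ANCOVA is valid without this covariate, its 95% interval already allows for chance imbalance, and the existing list is short and sensible: baseline outcome, the stratification factor and age. That stands. The omission costs efficiency and conditional balance, and does not bias the result.

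A second reply is that the prognostic effect is assumed. The medication rules in Section 6.5.1 adjust treatment toward glucose and HbA1c targets, which would tend to narrow any gap between insulin users and others. That also stands, and it is why the 0.3-point case belongs in the range.

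A reader might infer something stronger from Section 4.3: that the protocol itself says insulin use changes the result of this model. It does not. The sentence reads "e.g., including people on insulin), an ARR of 20% is still superior", set against the 33% of the cited trial. It is a hypothetical about remission, which the ANCOVA does not analyse. A smaller remission benefit in a population that includes insulin users would also be effect modification, which a main-effect covariate does not address. No section says that insulin use changes weight loss, and for HbA1c the link is only indirect, through tailored follow-up and medication adjustment.

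A reader might also measure the shift against the 0.44-point HbA1c difference in Section 2.2. That figure is a 2-year result from a trial without insulin users, so it is not this trial's expected effect.

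Finally, diabetes duration is recorded too: "diabetes diagnosis (duration of diabetes) and co-morbid conditions will be captured by interview". But the documents tie it to no HbA1c effect, and Section 5.1 already limits it to 6 years, so there is no comparable case for adding it.

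**Conclusion.** The point holds as a cheap improvement to one secondary analysis. The text supports the gap: a covariate list meant to control imbalance omits a recorded baseline factor that the protocol uses to tailor care. The benefit lies between negligible (about 2% of residual variance or less at a 0.3-point effect) and useful (4–21% at 0.5–1.0 points), with 20–30% users. Conditional shifts are usually well under half a standard error. Every HbA1c figure rests on the assumed prevalence, effect and residual SD. If insulin users turn out to be few or weakly different, little is gained. The documents do not support reading this as bias, as an invalid analysis or as a threat to the primary weight outcome.

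**What to change.** In Section 9.4.1, add baseline insulin use (yes/no) to the covariates of the 12-month HbA1c ANCOVA, alongside baseline HbA1c, gender and age, and derive it from the baseline medication record in Section 8.1. Leave randomization and the primary weight model as they are, and do not add diabetes duration.

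The cost is one sentence and one degree of freedom, with no new data. The wording should be settled before outcomes are seen by arm, because adding the covariate after an imbalance has been noticed would be post hoc.

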Study Population:	Participants will be individuals 18 and older who have T2DM diagnosed within the past 6 years with a BMI of 27-50 kg/m ² . Participants must have an HbA1c between 6.5-11.9%. Sample size will be 30 participants per treatment group.
Phase* or Stage:	Phase 4
Description of Sites/Facilities Enrolling Participants:	Wake Forest Baptist Health Weight Management Center (WMC) Wake Forest Baptist Health Diabetes Center (DC)
Description of Study Intervention/Experimental Manipulation:	Participants randomized to the HIWL treatment group will be placed on a meal replacement-based weight loss protocol. Our active intervention will be delivered with the aid of a technology platform that will automate portions of the intervention and assist clinicians in tailoring treatment and responding to participant needs in a “just-in-time” manner that we frame as a “data-assisted approach.”
Study Duration*:	15 months
Participant Duration:	12 months

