Even when T2DM is well controlled, significant risks and negative impacts associated with living with T2DM still remain. A recent systematic review showed that there was a 30% relative risk increase for severe hypoglycemia when attempting to achieve intensive glycemic control without any significant improvements in risk for all-cause and cardiovascular mortality.¹³ In 5 years, the ACCORD trial reported 19% more deaths in the intensive glucose-management group than in the standard glucose-management group.¹⁴ Recent reports have identified increased risk of all-cause mortality with intensification of T2DM treatment when adding insulin to metformin, raising questions about risks associated with insulin therapy.¹⁵ Additionally, the impact of T2DM on quality of life can be significant. Norris et al pooled data from 118 studies that assessed health related quality of life in persons with T2DM, finding that all 8 component scores of the Short Form-36 were lower than comparable U.S. population norms.¹⁶

We know that diabetes remission can be achieved with significant weight loss in the right patient populations. The landmark DiRECT trial demonstrated that long-term remission of T2DM can be achieved with the use of a total meal replacement diet and achievement of >10% weight loss.¹⁷ After 1 year of treatment, those in the intervention group had a mean weight loss of 10% compared to no weight loss for the control group. The rate of diabetes remission, defined as an hemoglobin A1c of <6.4% was 46% in the treatment group compared to 4% in the control arm. Remission was achieved in 86% of participants who lost at least 15 kg. At 2 years of follow up, the intervention group maintained a lower body weight (-5.4 kg [95% CI, -6.9 to -4]) and HbA1c (-0.44% [-0.76 to -0.13]); the rate of diabetes remission at 2 years was 36% for the intervention group compared to 3% for the control group (aOR 25.82, 8.25 to 80.84; p<0.0001).¹⁸ Participants in this trial were 20-65 years old, had T2DM for <6 years, BMI 27-45 kg/m², and were not on insulin.¹⁷

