4 STUDY DESIGN

4.1 OVERALL DESIGN

This project will determine if a data-assisted, high intensity medical weight loss intervention (HIWL) will lead to significant weight loss and diabetes remission in individuals with a BMI 27-50 kg/m² with T2DM of less than 6 years as compared to a diabetes self-management education intervention (DSME). Complete diabetes remission is considered to be achieved when the patient is not taking any anti-diabetes medication for at least 12 months, and the HbA1c is < 5.7%. Partial remission is achieved when the patient is not taking any anti-diabetes medication and has an HbA1c of 5.7-6.4% for at least 12 months. Using a randomized controlled study design, we will randomly assign 90 participants to HIWL, HIWL + CGM, or DSME. Participants assigned to HIWL will receive a high intensity behavioral weight loss intervention delivered using a digital patient engagement platform. Participants will be prescribed a low calorie dietary plan and a recommended physical activity program designed to produce 15-20% weight loss over 12 months. Those assigned to HIWL + CGM will receive the same intervention as HIWL; in addition we will provide them with CGM to use as part of their remote monitoring on a daily basis. Those assigned to DSME will participate in a comprehensive diabetes education program designed to provide education and skills for optimal diabetes management plus lifestyle modification counseling to produce 5% weight loss over the same timeframe. The primary outcome of weight loss will be assessed at 12 months.

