9 STATISTICAL CONSIDERATIONS

9.1 STATISTICAL HYPOTHESES

1. Test the effectiveness of the combined interventions (data-assisted approach for high intensity medical weight loss) for weight loss in a group of adults with recently diagnosed type 2 diabetes compared to standard of care diabetes self-management education.
H1- The data-assisted approach for HIWL (with or without CGM) will lead to 12% greater weight loss compared to the standard of care DSME.
2. Assess the impact of the data-assisted approach for high intensity medical weight loss on glycemic control outcomes including hemoglobin A1c and diabetes remission rates compared to diabetes self-management education.
H2a- The data-assisted approach for HIWL (with or without CGM) will lead to greater reduction in HbA1c compared to DSME.
H2b- The data-assisted approach for HIWL (with or without CGM) will lead to a greater proportion of participants achieving diabetes remission ($\text{HbA1c} < 6.5\%$) compared to DSME.
3. Explore impacts of adding CGM to the HIWL intervention on time to achieve A1c goals and participant satisfaction.
H3a- The HIWL + CGM approach will achieve A1c goals in a shorter timeframe than HIWL alone.
H3b- Participant satisfaction will be equivalent between the HIWL and HIWL + CGM approaches.
4. Explore differences in healthcare utilization between the treatment groups.
H4- The HIWL groups will have lower healthcare utilization compared to standard of care DSME.

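### The odds ratio is a fragile main summary for remission: at the control rates the protocol cites, about 3 to 5 trials in 10 would have no finite estimate, and the plan is silent on missing remission status

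*Combined protocol and SAP*

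**What the plan says.** Section 9.4.1 gives the whole remission analysis in one sentence: "The proportion of remission between two groups will be compared using a two-sided chi-square test and summarized using an odds ratio (OR"), plus confidence intervals. It names no strata, covariates, exact or penalised method, or procedure for an empty cell. The covariates listed in that section (baseline value, gender, age) belong to the ANCOVA of the continuous 12-month outcomes.

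The design has three arms: "we will randomly assign 90 participants to HIWL, HIWL + CGM, or DSME" (Section 4.1), and "Sample size will be 30 participants per treatment group" (Section 1.1). Hypothesis H2b reads: "The data-assisted approach for HIWL (with or without CGM) will lead to a greater proportion of participants achieving diabetes remission" compared with DSME (Section 9.1). This suggests pooling the two HIWL arms but does not say so. On allocation, Section 6.3 states: "Randomization will be done in blocks of 10, stratified by sex".

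For expected rates, Section 2.2 reports that remission in the cited trial at 1 year "was 46% in the treatment group compared to 4% in the control arm", and that "the rate of diabetes remission at 2 years was 36% for the intervention group compared to 3% for the control group". Section 4.3 considers a smaller effect in a broader population, saying that "an ARR of 20% is still superior to the Diabetes Prevention Program".

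Section 9.2 anticipates 10% loss to follow-up and allows for 20%. Section 9.3 analyses those randomised who receive the intervention. Section 7.1 keeps people who stop the intervention in follow-up. No section says how an unknown 12-month remission status is classified.

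**The concern.** With about 30 controls and a remission rate of 3% to 4%, about one DSME remission is expected. An odds ratio has no finite value when that count is zero, and it is barely informative when the count is one. Pooling the HIWL arms does not help, because the empty cell is in the control arm. With no sparse-data method named in advance, the team would have to choose one after seeing the table.

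Two further gaps affect the same result. Remission is not adjusted for sex or baseline HbA1c, although Section 9.4.1 justifies adjusting the continuous outcomes by the small sample. And with 10% to 20% loss expected, the observed rate depends on whether people with unknown status are dropped or counted as not in remission.

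Remission is a secondary endpoint, but it is in the trial's title and is the main cost-effectiveness outcome in Section 8.1.

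**Working it through.** **The plan's own figure.** Section 9.2 claims more than 95% power for weight loss (15% vs 3%, SD 6.8%, 30 per arm). At two-sided alpha 0.05 (assumed, as none is stated), power exceeds 99.99% with 30, 27 or 24 per arm, so the claim holds as a lower bound. The document gives no power figure for remission.

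**Inputs.** There are 30 controls (Section 1.1), which becomes 30 × 0.9 = 27 or 30 × 0.8 = 24 after the losses in Section 9.2. The control rate *p* is 4% or 3% (Section 2.2). No DSME-specific rate is given, so 5% and 10% are added as assumptions.

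**Chance of no DSME remission**, (1 − *p*)^*n*:

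| *p* | *n* = 30 | *n* = 27 | *n* = 24 |
|---|---|---|---|
| 3% | 0.97^30 = 40.1% | 43.9% | 0.97^24 = 48.1% |
| 4% | 0.96^30 = 29.4% | 33.2% | 0.96^24 = 37.5% |
| 5% (assumed) | 21.5% | 25.0% | 29.2% |
| 10% (assumed) | 4.2% | 5.8% | 8.0% |

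The chance of zero or one DSME remission is 66% (*n* = 30) to 75% (*n* = 24) at 4%, and 18% to 29% at 10%.

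**Illustration with one control event**, 28/60 (47%, close to the cited 46%) vs 1/30:
- Odds ratio = (28 × 29)/(32 × 1) = 25.4. SE of the log odds ratio = √(1/28 + 1/32 + 1/1 + 1/29) = 1.05. 95% CI = exp(3.23 ± 1.96 × 1.05) = 3.2 to 198.
- Risk difference = 46.7% − 3.3% = 43.3 points. The Wilson limits are 34.6% to 59.1% and 0.6% to 16.7%. The Newcombe interval combines them into 25 to 56 points.

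**Illustration with no control event**, 28/60 vs 0/30:
- Odds ratio: infinite. The conditional exact 95% interval runs from 5.8 to infinity. Adding 0.5 to each cell gives 53 (3.1 to 915).
- Risk difference: 46.7 points (Newcombe 30 to 59).
- Uncorrected chi-square = 20.3, p = 7 × 10⁻⁶, smallest expected count 30 × 28/90 = 9.3. The test itself still works.

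**Behaviour of the chi-square by exact enumeration.** At 46% vs 4%, power is 98.9% (30 vs 30) and 96.9% (24 vs 24). At 24% vs 4%, which is the 20-point effect in Section 4.3 added to the cited control rate, power is 67% (30 vs 30) and 74% (60 vs 30), and an expected count falls below 5 in 68% and 39% of trials. Under the null with 30 vs 30, the rejection rate is 1.0% at 3%, 1.9% at 4% and 5.4% at 10%.

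**Missing status.** Eleven remissions are 11/24 = 46% of completers at 20% loss, but 11/30 = 37% of those randomised. At the anticipated 10% loss, 46% of completers corresponds to 0.46 × 0.9 = 41% of those randomised. Counting missing as non-remission does not cure the sparsity: with 30 controls and a true rate of 4%, the zero-cell chance is (1 − 0.04 × 0.9)^30 = 33% at 10% loss and (1 − 0.04 × 0.8)^30 = 38% at 20% loss.

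**The case against.** The strongest reply is that the specified test survives. The chi-square is valid without covariates in a randomised trial, works with an empty control cell, and has high power at the cited rates. Section 9.4.1 does not commit to a Wald interval, so an exact one-sided statement about the odds ratio is available. All of this stands. A reader might infer that the remission result would be unreportable or the test invalid, and the documents do not support that. What is lost is a finite odds ratio and upper limit.

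Second, the 4% is borrowed. It comes from controls who lost no weight, while DSME prescribes an energy deficit (Section 6.1.1), aims for 5% weight loss (Section 4.1) and is assumed to achieve 3% (Section 9.2). This also stands: the frequency is conditional, and at 10% the problem is uncommon. The rate also depends on the remission definition, which differs between Sections 1.1, 3, 4.1, 8.1 and 9.1.

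Third, Section 9.4.1 describes its aim as estimating differences in the proportion remitting and promises 95% intervals for intervention effects generally. A risk difference may therefore already be intended. That supports the fix, since the odds ratio is the only summary actually named.

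Finally, a reader might infer that dropouts will be excluded, or that the two-group wording contradicts the three-arm design. The plan states neither. It declares intention to treat and continued follow-up, and pooling is the natural reading of H2b. These are silences to fill, not stated rules that are wrong.

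**Conclusion.** The concern holds as a weakness in the choice of summary measure and as a gap in specification. If the DSME rate is near the cited 3% to 4%, the sample odds ratio has no finite value in 29% to 48% of trials with 24 to 30 controls, and its interval is very wide when one control remits. If the rate is nearer 10%, the zero-cell figure is 4% to 8%. The conclusion rests on the borrowed control rate and the planned arm size. It does not depend on whether the HIWL arms are pooled.

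Leaving out sex and baseline HbA1c gives up precision and is inconsistent with the continuous analyses, but does not make the test invalid. The missing-status rule should be written down because it can move an observed rate by about 5 points at 10% loss and 9 points at 20% (46% to 41% or 37%).

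**What to change.** Amend Section 9.4.1 before outcome data by arm are seen:
- **Main estimate:** risk difference in any remission (partial plus complete), both HIWL arms pooled vs DSME, in all randomised participants, with a sex-stratified score-type interval (for example Miettinen-Nurminen or stratified Newcombe).
- **Test:** Mantel-Haenszel, stratified by sex.
- **Supportive:** odds ratio from a Firth-penalised logistic model with arm, sex and baseline HbA1c.
- **Missing 12-month status:** count as non-remission, with multiple imputation of HbA1c and medication status as a sensitivity analysis.

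The cost is SAP wording only, with no new data. The risk difference also matches the scale of the absolute-risk argument in Section 4.3 and the cost-effectiveness denominator in Section 9.4.1. The downsides are that reported remission rates may be slightly lower, and that the missing-status rule is itself an assumption and leaves the control counts just as sparse.
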